14.2 Clinical Laboratory Variables

Clinical laboratory tests are performed at Baseline, Week 2, Week 6, Week 12, week 20, Week 28, Week 36, Week 44 and Week 52 visits.

Due to COVID-19 disruptions it is possible that some test results may be collected from a local laboratory. Local laboratory results and the associated normal ranges will be converted to SI units; the local laboratory results, in SI units, will then be normalized to central lab ranges to be included in summary data analysis together with the central laboratory results. The normalization will be performed using the following scale transformation equation:

$$s = L_s + (x - L_x) \frac{U_s - L_s}{U_x - L_x}$$

where s is the normalized individual laboratory value to be used for summary; x is the original value from the local lab; L_x and U_x are the lower and upper limits from the local lab; L_s and U_s are the lower and upper limits from the central lab.

For labs with only a single upper (or lower) limit, the following scale transformation equation will be used:

$$s = x \frac{U_s}{U_x}$$

where s is the normalized individual laboratory value to be used for summary; x is the original value from the local lab; U_s is the upper (or lower) limit from the central lab; U_x is the upper (or lower) limit from the local laboratory. Local laboratory results and normalized results will be included in data listings. Only central lab and normalized local lab results will be used for summary of change from baseline, shift, and potentially clinically important (PCI) analyses.

Clinical laboratory tests include the following:

- Clinical chemistry serum tests
 - Sodium (Na), potassium (K), carbon dioxide (CO₂), chloride (Cl), phosphorus (P), calcium (Ca), blood urea nitrogen (BUN), creatinine (CR), glucose, albumin (ALB), total protein

- Alanine aminotransferase (ALT), aspartate aminotransferase (AST), gamma-glutamyl transpeptidase (GGT), alkaline phosphatase (ALP), total bilirubin (TBIL), lactate dehydrogenase (LDH)
- Lipid panel
 - Total cholesterol, high-density lipoprotein (HDL)-cholesterol, triglycerides, low-density lipoprotein (LDL)-cholesterol, cholesterol/HDL ratio, non-HDL cholesterol
- HbA_{1c}
- Prolactin
 - Prolactin results should be blinded to the Investigator and the Sponsor at Baseline. Results will be monitored by an independent Medical Monitor from the Clinical Research Organization (CRO).
- Creatine kinase (CK)/creatine phosphokinase (CPK)
- Pregnancy test
 - A urine pregnancy test should be performed at all designated visits for women of child-bearing potential. If positive, the result will be confirmed with a serum pregnancy test.
 - If urine cannot be obtained in women of childbearing potential, a serum pregnancy test should be done in its place
- Hematology tests
 - Complete blood count (CBC) including:
 - White blood cell (WBC) count
 - Complete differential (relative and absolute)
 - Hematocrit, hemoglobin, red blood cells (RBC), platelets
 - Reticulocyte count
- Urinalysis
 - Blood, RBCs, WBCs, protein, glucose, ketones, specific gravity, pH
- Urine toxicology screen

- Urine toxicology screen will test for controlled substances. The following controlled substances may be tested with a urine toxicology screen: amphetamine, barbiturates, benzodiazepines, cocaine, methadone, morphine/opiates, methamphetamine, marijuana (tetrahydrocannabinol), phencyclidine, ecstasy (3,4-methylenedioxymethamphetamine).
- Subjects who test positive and have a valid prescription for a controlled substance may be retested if they agree to abstain from the medication for the length of their participation in the study.

14.2.1 Analysis of Clinical Laboratory Variables

14.2.1.1 Observed Values and Change from Baseline

All laboratory test results will be provided in the listings. The listings will include date and study day of collection. All units will be displayed in Système International [SI] units. Out of range values will be flagged in the data listings (e.g. 'L' or 'H').

Clinical laboratory values for hematology, chemistry and urinalysis will be summarized using descriptive statistics at Baseline, Week 3 and Week 6. The change from Baseline values will also be summarized at Week 3 and Week 6. The overall minimum and maximum post-baseline observed and change from Baseline values will also be summarized. For hemoglobin, hematocrit and uric acid, the above summaries will be presented for each gender as well as for both genders combined. For urinalysis with categorical results (blood, protein, glucose, and ketones), the number and percentage of subjects will be tabulated by category at Baseline, Week 3 and Week 6, with the denominator being the number of subjects with non-missing values for the given parameter, visit and cohort.

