5.1.1 Change from Baseline Summaries

Change from Baseline results for each continuous measure in the safety and efficacy analyses will be presented in two ways:

1. Main analysis: using the Baseline from ACP-103-070 (study -070) and reporting the changes across study -070 timepoints
2. Exploratory analysis: using the Baseline from the antecedent study (ACP-103-069) and reporting the changes across the timepoints of both the antecedent study and the open-label study -070.

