5.3.2 Analysis Visit Windows

The Baseline value is defined as the most recent non-missing value collected prior to the administration of the first dose of open-label study drug.

Efficacy and safety assessments will be summarized by analysis visits as presented in [Table 2](#) below.

Table 2 Analysis Visit Windows

Open-label (OL) Analysis Visit Name	Target Study Day ¹	Study Day Interval
OL Baseline	1	≤ 1
OL Week 2	15	2 to 28
OL Week 6	43	29 to 63
OL Week 12	85	64 to 112
OL Week 20	141	113 to 168
OL Week 28	197	169 to 224
OL Week 36	253	225 to 280
OL Week 44	309	281 to 336
OL Week 52	365	≥ 337

¹ If the assessment date \geq first OL dose date, study day = assessment date - first OL dose date + 1, otherwise study day = assessment date – first OL dose. Study day 1 is the first OL dose date.

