5.3.3 Unscheduled Assessments

Both scheduled and unscheduled assessments, including early termination visits, will be considered for planned timepoint analyses based on the above analysis visit windowing rules. All assessments will be presented in data listings.

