19 CHANGES TO ANALYSES SPECIFIED IN PROTOCOL

No changes have been made to the analyses as specified in the protocol.

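### SAP 14.2.1.1 summarises laboratory values at Weeks 3 and 6, when no safety laboratory tests are scheduled, and omits Weeks 12, 28, 44 and 52, when they are

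*SAP*

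**What the plan says.** SAP 14.2.1.1 fixes the visits for the laboratory tables in three sentences:

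- descriptive statistics: "Clinical laboratory values for hematology, chemistry and urinalysis will be summarized using descriptive statistics at Baseline, Week 3 and Week 6";
- change from Baseline: "The change from Baseline values will also be summarized at Week 3 and Week 6";
- categorical urinalysis (blood, protein, glucose, ketones): "the number and percentage of subjects will be tabulated by category at Baseline, Week 3 and Week 6".

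The general rules differ. For each continuous safety and efficacy measure, the main analysis in SAP 5.1.1 is "using the Baseline from ACP-103-070 (study -070) and reporting the changes across study -070 timepoints". SAP 5.3.2 adds: "Efficacy and safety assessments will be summarized by analysis visits as presented in" Table 2. That table has open-label windows for Weeks 2, 6, 12, 20, 28, 36, 44 and 52, and none for Week 3.

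SAP 14.2 gives a further schedule. It begins "Clinical laboratory tests are performed at Baseline, Week 2, Week 6, Week 12, week 20" and goes on through every remaining clinic visit to Week 52. Protocol Table 6-1, Protocol Table S-1 and SAP Appendix 21.1 instead place these tests at Baseline and Weeks 12, 28, 44 and 52 only.

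**The concern.** Laboratory tests belong to the safety evaluation under the primary objective, which is safety over 52 weeks. The SAP gives incompatible instructions on which visits carry the observed-value and change tables for glucose, HbA1c, lipids, prolactin and liver tests. A rule specific to laboratory data is normally read as overriding a general one. A programmer who follows it would produce no by-visit means and no Week 52 change from Baseline for any analyte.

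The Week 6 row would not simply be empty. SAP 5.3.3 says: "Both scheduled and unscheduled assessments, including early termination visits, will be considered for planned timepoint analyses". Samples from children who stopped early, or who were tested out of schedule for a clinical reason, would fill that row. They are a selected subset, shown under a label that suggests a planned visit.

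The antecedent double-blind study lasted 6 weeks (Protocol 1.4.1), so the wording may have been carried over from its SAP. That is an inference, and the point does not depend on it. The sections on vital signs, ECG, physical examination and Tanner staging (SAP 14.3 to 14.5) do use this study's visits.

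**Working it through.** **1. Which visits have safety laboratory tests?** Protocol Table 6-1 lists chemistry, blood count and urinalysis at Visits 1, 4, 6, 8 and 9: Baseline and Weeks 12, 28, 44 and 52 (Visit 9 also serves as the early-termination visit). The blood volumes give an independent check. Per-visit volumes are in Protocol Tables 6-3 and 6-4, and the stated totals are in Protocol 6.5.

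- Ages 6 to 17: 5 × 8 mL = 40 mL (stated: 40 mL).
- Age 5: 5.9 + 4 × 6.3 = 31.1 mL (stated: 31.1 mL).

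Both totals are reproduced, so five draws is the whole schedule. The list in SAP 14.2, with tests at all nine visits, does not fit it.

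**2. Set the three sources side by side.**

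| Week | SAP Table 2 window (study days) | Chemistry, blood count, urinalysis scheduled | Summarised under SAP 14.2.1.1 |
|---|---|---|---|
| 2 | 2–28 | no | no |
| 3 | none | no (not a visit) | yes |
| 6 | 29–63 | no | yes |
| 12 | 64–112 | yes | no |
| 20 | 113–168 | no | no |
| 28 | 169–224 | yes | no |
| 36 | 225–280 | no | no |
| 44 | 281–336 | yes | no |
| 52 | 337 onward | yes | no |

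The sets {3, 6} and {12, 28, 44, 52} do not overlap. Week 3 would be Day 7 × 3 + 1 = 22, which Table 2 assigns to Week 2, so no value can carry a Week 3 label.

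**3. Could an on-schedule Week 12 sample reach the Week 6 row?** The first dose is the day after the Baseline visit, so 84 days after Baseline is Study Day 84. The Table 2 target is Day 85. Allowing ±3 days around either gives Days 81 to 88. The Week 6 window closes at Day 63, and 81 − 63 = 18 days, so the answer is no. The last window that the rule names closes 63/364 = 17% of the way through the treatment period.

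**4. Do the proposed visits work?** With target days 85, 197, 309 and 365 and a range of −4 to +3 days, samples fall at Days 81–88, 193–200, 305–312 and 361–368. Each range lies wholly inside its own Table 2 window.

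**5. Eosinophil limit in SAP Table 3.** The row gives 10 or more both in percent and in L/L. A fraction cannot exceed 1. The same table converts hematocrit 50% to 0.50 L/L and HbA1c 7% to 0.07 L/L, so 10% corresponds to 0.10 L/L. If the SI column is programmed, no subject can be flagged. If the percent column is used, there is no effect.

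**The case against.** The strongest reply is that little is at risk. The analyses are descriptive, with no hypothesis tests. By-visit PCI counts, by-visit shifts, overall minimum and maximum values and listings all use the later data. The Week 3 instruction cannot be executed, so it would surface at programming. SAP 5.1.1 already supplies the right timepoints, and the table specifications are in a separate document. All this is true, and it limits the severity. It does not remove the fault. Extremes carry no time course, and PCI and shift counts can miss a gradual change in the mean within the normal range. A silent correction at programming would also depart from the approved SAP, and Protocol 9.1 requires such departures to be described and justified.

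Two narrower objections stand in part.

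- The conflict with SAP 5.3.2 is direct only for Week 3. Week 6 is a Table 2 visit; its fault is that no safety laboratory tests are scheduled there.
- Protocol 9.5.2 requires laboratory values and changes by timepoint, while SAP 19 states: "No changes have been made to the analyses as specified in the protocol". The SAP is based on Amendment 3.0 of 21 December 2022, whereas the supplied protocol synopsis is dated 29 February 2024, so this comparison may cross versions. The conflicts with SAP 5.1.1 and SAP Appendix 21.1 are enough without it.

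The wording slip in SAP 14.2.1.2 and the eosinophil limit are real but secondary, and add no weight to the main point.

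**Conclusion.** The concern holds. The laboratory-specific rule covers 0 of 4 scheduled post-baseline laboratory visits, and neither of its two named weeks has a scheduled safety laboratory test. What would be missing is the by-visit descriptive statistics, the by-visit change from Baseline and the urinalysis category tables, including those at Week 52. The data are still collected and still appear in the other laboratory outputs.

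This should be fixed before the tables are produced. It affects the completeness of reporting for the primary safety objective; it is not a matter of error control. The conclusion assumes that the SAP text is followed as written. The separate table specifications are not available, so the final output cannot be confirmed.

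**What to change.** - **SAP 14.2.1.1:** replace Week 3 and Week 6 with Weeks 12, 28, 44 and 52 in all three sentences.
- **SAP 14.2:** align the opening sentence with Protocol Table 6-1 and SAP Appendix 21.1.
- **SAP 14.2.1.2:** the opening sentence refers to a scheduled post-baseline minimum. Change it to scheduled post-baseline visits, which is what the by-visit denominator later in that section already assumes.
- **SAP Table 3:** set the SI eosinophil limit to 0.10 L/L, to match the stated 10%.

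It would help to add a sentence saying that unscheduled and early-termination samples falling in the Week 2, 6, 20 or 36 windows get no by-visit row but stay in the overall minimum and maximum, the overall PCI counts and the listings.

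The cost is SAP wording and a check that the table specifications agree. No new data are needed.

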14.2.1.2 Shift Tables

Laboratory values will be summarized in shift tables to determine the number and percentage of subjects with values classified as below (low), within (normal), and above (high) normal ranges at scheduled post-baseline minimum relative to the same classification at the Baseline visit. The shifts from Baseline to overall post-Baseline minimum and overall post-Baseline maximum will also be presented, only for the open-label treatment period. For the by-visit shift summary, the denominator is the number of subjects with non-missing values at Baseline and the given visit for the given parameter and cohort. For the shift to the overall post-baseline minimum or maximum, the denominator is the number of subjects with non-missing Baseline and at least one post-baseline value for the given parameter and cohort. For hemoglobin, hematocrit and uric acid, the shift summaries will be presented for each gender as well as for both genders combined.

14.2.1.3 Potentially Clinically Important (PCI) Laboratory Values

The number and percentage of subjects with PCI laboratory values at scheduled post-Baseline visits and overall post-Baseline (for the open-label treatment period) will be summarized by Baseline status (all and within normal range) for selected parameters. PCI criteria are listed in [Table 3](#) and [Table 4](#). For the overall post-baseline summaries of PCI values, all post-baseline values will be considered, including unscheduled and out of window values. Subjects with multiple PCI values for a given parameter will be counted only once for that parameter. For the by-visit summary, the numerator for the percentage is the number of subjects with a post-baseline PCI value for the given parameter, visit and cohort, and the denominator is the number of subjects with non-missing values for the given parameter, visit and cohort. For the overall post-baseline summary, the numerator for the percentage is the number of subjects with at least one post-baseline PCI laboratory value for the given parameter and cohort, and the denominator is the number of subjects with at least one post-baseline laboratory value for the given parameter and cohort. For hemoglobin, hematocrit and uric acid, the count and percentage of subjects with PCI values will be presented for each gender as well as for both genders combined. A listing of all PCI values in study -070 will be provided. This listing will include all observations from study -070 for those subjects and parameters for which at least one PCI value (including Baseline) was observed.

Table 3 Criteria for Potentially Clinically Important Laboratory Values – Hematology and Chemistry

Analyte	Conventional Unit	Low PCI Criteria	High PCI Criteria	SI Unit	Low PCI Criteria	High PCI Criteria
Hematology (whole blood)						
Hemoglobin (male)	g/dL	<11	>17	g/L	<110	>170
Hemoglobin (female)	g/dL	<10	>17	g/L	<100	>170
Hematocrit	%	<30	>50	L/L	<0.3	>0.50
Leukocyte (White Blood Cell Count)	x 10 ³ /uL	≤2.8	≥15	x 10 ⁹ /L	≤2.8	≥15
Neutrophils	x 10 ³ /uL	≤1.5	No upper limit	x 10 ⁹ /L	≤1.5	No upper limit
Eosinophils	%	No lower limit	≥10	L/L	No lower limit	≥10
Platelet Count	x 10 ³ /uL	≤75	≥700	10 ⁹ /L	≤75	≥700
Chemistry (serum or plasma)						
ALT (SGPT)	U/L	No lower limit	≥3 X ULN	U/L	No lower limit	≥3 X ULN
AST (SGOT)	U/L	No lower limit	≥3 X ULN	U/L	No lower limit	≥3 X ULN
Total Bilirubin	mg/dL	No lower limit	≥1.5 ULN	umol/L	No lower limit	≥1.5 ULN
BUN	mg/dL	No lower limit	≥30.0	mmol/L	No lower limit	≥10.71
Creatine Kinase (CPK)	U/L	No lower limit	≥3 ULN	U/L	No lower limit	≥3 ULN
Sodium	mEq/L	≤125	≥155	mmol/L	≤125	≥155
Potassium	mEq/L	≤3.0	≥5.5	mmol/L	≤3.0	≥5.5
Calcium, total	mg/dL	<8.0	>11.0	mmol/L	<2.0	>2.75
Lactate Dehydrogenase (LDH)	U/L	No lower limit	≥3 X ULN	U/L	No lower limit	≥3 X ULN
Alkaline Phosphatase	U/L	No lower limit	≥3 X ULN	U/L	No lower limit	≥3 X ULN
Uric acid	mg/dL	No lower limit	≥8.5	umol/L	No lower limit	≥505.75
Albumin	g/dL	≤2.6	≥6.0	g/L	≤26	≥60
Total Protein	g/dL	≤5.0	≥10.0	g/L	≤50	≥100
Chloride	mEq/L	≤85	≥120	mmol/L	≤85	≥120
Glucose (random)	mg/dL	≤45.1	≥115.0	mmol/L	≤2.48	≥6.4
Serum Creatinine	mg/dL	Not Applicable	>1.5 ULN	umol/L	Not Applicable	>1.5 ULN
Triglycerides	mg/dL	Not Applicable	>300	mmol/L	Not Applicable	>3.39
Gamma-Glutamyl Transferase (GGT)	U/L	Not Applicable	≥3 ULN	U/L	Not Applicable	≥3 ULN
Phosphorus, inorganic	mg/dL	≤1,0	≥7	mmol/L	≤0.32	≥2.26
Magnesium	mEq/L	≤0.7	≥5.0	mmol/L	≤0.35	≥2.5

Table 3 Criteria for Potentially Clinically Important Laboratory Values – Hematology and Chemistry (Continued)

Total Cholesterol, Fasting	mg/dL	No lower limit	≥ 240	mmol/L	No lower limit	≥ 6.21
Hb1Ac	%	No lower limit	≥ 7	L/L	No lower limit	≥ 0.07

Table 4 Criteria for Potentially Clinically Important Laboratory Values - Urinalysis

Urinalysis (qualitative dipstick)	Low PCI Criteria	High PCI Criteria
Blood (occult blood)	Not Applicable	\geq Moderate or +2 (Q2)
Protein	Not Applicable	≥ 100 mg/dL (ICON) or +2 (Q2)
Glucose	Not Applicable	≥ 500 mg/dL (ICON) or +2 (Q2)

The pregnancy results (positive or negative) for female subjects of childbearing potential and the urine drug screen results will be presented in a listing.

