## Appendix C Criteria for Identifying Potentially Clinically Important Laboratory Values

Analyte	Conventional Unit	Low PCI Criteria	High PCI Criteria
Hematology (whole blood)			
Hemoglobin (Male)	g/dL	<11	>17
Hemoglobin (Female)	g/dL	<10	>17
Hematocrit (Both)	%	<30	>50
Leukocyte (White Blood Cell Count)	× 10  /uL	≤2.8	≥15
Neutrophils	× 10  /uL	≤1.5	No upper limit
Eosinophils	%	≥10%	No lower limit
Platelet Count	× 10  /uL	≤75	≥700
Chemistry (serum or plasma)			
ALT (SGPT)	U/L	No lower limit	≥3 × ULN
AST (SGOT)	U/L	No lower limit	≥3 × ULN
Gamma-Glutamyl Transferase (GGT)	U/L	No lower limit	≥3 ULN
Lactate Dehydrogenase (LDH)	U/L	No lower limit	≥3 × ULN
Alkaline Phosphatase	U/L	No lower limit	≥3 × ULN
Total Bilirubin	mg/dL	No lower limit	≥1.5 ULN
CPK	mg/dL	No lower limit	≥3 ULN
BUN	mg/dL	No lower limit	≥30.0
Serum Creatinine	mg/dL	Not Applicable	>1.5 ULN
Sodium	mEq/L	≤125	≥155
Potassium	mEq/L	≤3.0	≥5.5
Calcium, total	mg/dL	<8.0	>11.0
Chloride	mEq/L	≤85	≥120
Phosphorous, inorganic	mg/dL	≤1.0 mg/dL	≥4.5 mg/dL
Magnesium	mEq/L	≤0.7 mEq/L	≥5.0 mEq/L
Uric acid	mg/dL	No lower limit	≥8.5
Albumin	g/dL	≤2.6	≥6.0
Total Protein	g/dL	≤5.0	≥10.0
Glucose (random)	mg/dL	≤45.1	≥115.0
Hb1Ac	%	No lower limit	≥7%
Total Cholesterol, Fasting	mg/dL	No lower limit	≥240 mg/dL
Urinalysis			
Blood (occult blood)		Not Applicable	≥ Moderate
Protein	mg/dL	Not Applicable	≥100 mg/dL
Glucose	mg/dL	Not Applicable	≥500 mg/dL

Abbreviations: ALT (SGPT)=alanine aminotransferase (serum glutamic-pyruvic transaminase);

AST (SGOT)=aspartate aminotransferase (serum glutamic-oxaloacetic transaminase); BUN=blood urea nitrogen; CPK=creatine phosphokinase; HbA1c=glycosylated hemoglobin; PCI=potentially clinically important; ULN=upper limit of normal.

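### SAP Table 3 prints the SI-unit PCI limit for eosinophils as 10 L/L, which no fraction can reach; 10% is 0.10 L/L

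*SAP*

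**What the plan says.** SAP Section 14.2.1.3 plans counts and percentages of subjects with PCI laboratory values, by visit and overall, and takes its criteria from Tables 3 and 4. Table 3 gives each limit twice, in conventional and in SI units. The eosinophil row is "Eosinophils % No lower limit ≥10 L/L No lower limit ≥10". Two other analytes in the table go from percent to L/L: "Hematocrit % <30 >50 L/L <0.3 >0.50" and "Hb1Ac % No lower limit ≥ 7 L/L No lower limit ≥ 0.07".

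On units, SAP Section 14.2.1.1 states "All units will be displayed in Système International [SI] units", in a paragraph about listings. For results from local laboratories, SAP Section 14.2 states "Local laboratory results and the associated normal ranges will be converted to SI units". Those results are then scaled to the central laboratory's ranges and used in the PCI analyses together with the central results. Section 14.2.1.3 does not say which unit column the flags use.

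Protocol Appendix C gives the eosinophil criterion in percent only: "Eosinophils % ≥10% No lower limit". The 10% entry stands in the Low PCI column and the no-limit entry in the High PCI column. For phosphorus, Appendix C has "Phosphorous, inorganic mg/dL ≤1.0 mg/dL ≥4.5 mg/dL", while SAP Table 3 has a high limit of ≥7 mg/dL (≥2.26 mmol/L).

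**The concern.** One row carries two criteria that should be equivalent but differ by a factor of 100, and the one in SI units cannot be met by any possible result. A program that compared eosinophil fractions with 10 would run without error and return zero at each visit and overall. The PCI listing is built from subjects and parameters with at least one PCI value, so eosinophils would be missing there too. Nothing in the output would tell a reader that the zero comes from the threshold and not from the children's blood counts.

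The study's primary objective is long-term safety. A complete differential is part of the hematology panel, and blood counts are scheduled at Baseline and Weeks 12, 28, 44 and 52. A planned safety screen on those data should be able to fire.

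**Working it through.** **Inputs.** From SAP Table 3: eosinophils ≥10% and ≥10 L/L; hematocrit <30% and >50%, with <0.3 and >0.50 L/L; HbA1c ≥7% and ≥0.07 L/L.

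**Step 1: the table's own conversion.** Fraction (L/L) = percent × 0.01.

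- Hematocrit: 30 × 0.01 = 0.30 and 50 × 0.01 = 0.50. Both match the table.
- HbA1c: 7 × 0.01 = 0.07. This matches.
- Eosinophils: 10 × 0.01 = 0.10. The table prints 10. Ratio: 10 / 0.10 = 100.

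Read backwards, 10 L/L is 10 × 100 = 1000%.

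**Step 2: is the SI column wrong elsewhere?** Twenty-four other numeric limits in Table 3 were converted with standard factors, which are not given in the documents. The ratio of printed to converted limit ran from 0.991 to 1.003, so all agree within 1%. Eosinophils is the only row out of line.

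**Step 3: effect on the flag.** Each whole percentage from 0 to 100 (101 values) was tested:

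| Criterion | Values flagged |
|---|---|
| ≥10% (conventional column) | 91 of 101 |
| ≥10 L/L (SI column as printed) | 0 of 101 |
| ≥0.10 L/L (converted) | 91 of 101 |

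The converted limit selects the same values, 10 to 100, as the conventional one. These counts show which results could be flagged; they do not estimate how many children would be.

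**Step 4: phosphorus.** With the factor 0.323, 7 mg/dL gives 7 × 0.323 = 2.261 mmol/L, which agrees with the 2.26 in Table 3, whereas 4.5 mg/dL would give 4.5 × 0.323 = 1.45. The SAP row is thus consistent within itself, and the gap to Appendix C is a difference in the limit, not a conversion slip. A value from 4.5 to just under 7 mg/dL is PCI under Appendix C and not under the SAP.

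**The case against.** The best defence is that the SAP never says the flags use the SI column. The sentence on SI display belongs to a paragraph on listings, the SI conversion concerns local-laboratory results, output specifications are in a separate document, and the PCI summary covers selected parameters without naming them. The ≥10% column in the same row works. If the differential is held in percent, the number 10 is right and only the L/L label is wrong. All of this stands, and it makes the zero rate conditional.

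Nor would high eosinophils vanish from the report. Listings flag values outside the normal range, shift tables classify them up to the post-baseline maximum, and overall maxima and changes are summarized. That also stands: what would be lost is the PCI screen, not the data.

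A reader might infer more in several places, and the documents do not support it:

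- *Appendix C flags in the wrong direction.* Its entry still says 10% or more, so it selects the same values as the SAP's conventional limit. Only the column is misplaced.
- *The phosphorus difference shows that the SAP's Section 19 is untrue.* That section says "No changes have been made to the analyses as specified in the protocol", but the SAP is based on protocol Amendment 3.0 of 21 December 2022 and the protocol at hand is dated 29 February 2024. Appendix C as it stood in Amendment 3.0 is not available for comparison.
- *The low-glucose SI limit is a second error of the same kind.* The printed 2.48 mmol/L is within 1% of the converted 2.503 and does not matter here.
- *The row is critical because the protocol mentions rash, urticaria and angioedema-type reactions.* The documents do not link these to eosinophil counts, and eosinophilia is not among the class effects listed for active monitoring. Such reactions are collected as adverse events in any case.

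**Conclusion.** The point holds in a limited form. The eosinophil SI limit in SAP Table 3 is 100 times the conventional limit beside it and cannot be reached. If the PCI flags are programmed from the SI column, the eosinophil PCI rate is 0% at every visit and overall, and eosinophils drop out of the PCI listing. SI programming is the likelier reading, given the SAP's SI displays and its conversion of local results, but it is an assumption. If percentages are compared with 10, nothing is lost.

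It is a minor correction. It affects one row of a descriptive output, with no hypothesis test attached, and it touches neither the primary endpoint (treatment-emergent adverse events) nor the secondary responder endpoint. It is worth making because the failure would be silent.

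The phosphorus mismatch is real between the two documents supplied and is a separate item. Nothing in them settles which limit was intended.

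**What to change.** 1. In SAP Table 3, change the eosinophil high limit in the SI column from ≥10 to ≥0.10 L/L, so that it equals the stated ≥10%. Confirm the unit in which the analysis data hold the differential, and state in Section 14.2.1.3 which unit column the PCI flags use.
2. In Protocol Appendix C, place the eosinophil ≥10% entry in the High PCI column and the no-lower-limit entry in the Low PCI column, as in the SAP.
3. Separately, reconcile the high phosphorus limit (≥4.5 mg/dL in Appendix C, ≥7 mg/dL in SAP Table 3), or record the difference and its reason in the SAP.

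The cost is a few words in the SAP, at most one constant in the PCI program, and a clerical correction to Appendix C. No new data, visits or samples are needed. The changes should be made before the PCI tables and listing are finalized.
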